The safety information in the HCP Guide provides context and risk management advice for key safety aspects of the SmPC, namely (key safety aspects with updates in the HCP Guide after Article 20 are listed in *italics*):

- Serious and opportunistic infections
- Herpes zoster
- Potential risk of birth defects if filgotinib is taken during pregnancy

- Potential risk of VTE
- Potential risk of MACE
- Potential risk of malignancy
- Prescribing in elderly patients and in patients with risk factors for VTE, MACE, and malignancy

The SmPC specifies that the recommended dose for induction treatment in UC is 200 mg once daily. The recommended dose for maintenance treatment is 200 mg once daily. In patients aged 65 years or older or at higher risk of VTE, MACE and malignancy, the recommended dose is 200 mg once daily for the induction treatment which may be prolonged up to Week 22, and 100 mg once daily for maintenance treatment. In case of flare of the disease, the dose may be escalated to 200 mg once daily. For long term treatment, the lowest effective dose should be used (as per SmPC Section 4.2 'Posology and method of administration').

In patients with active tuberculosis (TB), active serious infections, or in women who are pregnant treatment with filgotinib is contraindicated (as per SmPC Section 4.3 'Contraindications').

Additional aspects as per updated SmPC Section 4.4 'Special warnings and precautions for use' are listed below:

*Use in patients 65 years of age and older*: Considering the increased risk of MACE, malignancies, serious infections, and all-cause mortality in patients 65 years of age and older, filgotinib should only be used in these patients if no suitable treatment alternatives are available.

*Infections*: As there is a higher incidence of infections in the elderly and in the diabetic populations in general, caution should be used when treating the elderly and patients with diabetes.

*Malignancy*: In patients 65 years of age and older, patients who are current or past long-time smokers, or with other malignancy risk factors (e.g. current malignancy or history of malignancy), filgotinib should only be used if no suitable treatment alternatives are available.

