## 8.2.4. Index Date, Follow-up

The index date (= start of follow-up) in each registry will be the date a patient starts UC treatment with filgotinib (i.e. the date of first identification of filgotinib exposure in the registry) after the EC decision date. The patient's total follow-up time is defined as the time from the filgotinib index date until the earliest of treatment discontinuation, study withdrawal (withdrawn from the registry, death or loss to follow-up) or end of study.

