#### 8.3.3.3. SWIBREG (SWE)

Drug exposures for a small molecule such as filgotinib is captured in the Prescribed Drug Register ([PDR] i.e. all dispensed prescriptions of the drug). A dispensing will be assumed to last for 180 days, after which a lack of a new dispensed prescription will be counted as a treatment hiatus.

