#### 8.4.3. SWIBREG (SWE)

Baseline and follow-up data, including patient demographics, disease characteristics, and treatment will be based on data from SWIBREG and the Swedish Patient and Prescribed Drug Registers. SWIBREG data will be augmented with linkages to the Swedish Cancer, Contagious Diseases, Medical Birth, Causes of Death, and Total Population Registers.

Details of variables to be collected in SWIBREG can be found in Annex 3 – Table 5.

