#### Follow-up

Among women starting filgotinib, the number and proportion who become pregnant during follow-up will be reported. Similarly, the number and proportion of patients who have a new

diagnosis of TB during follow-up, a serious acute infection, a diagnosis of viral hepatitis, concomitant treatment with other immunosuppressants, or who are administered a live attenuated vaccine will be reported. In patients with TB, or a serious infection identified during follow-up, it will be assessed whether treatment was stopped or interrupted after the diagnosis. The proportion of patients who have a test for lipids at around 12 weeks since initiation of filgotinib will be reported.

Should a VTE event occur, subsequent changes to filgotinib use will be reported (filgotinib treatment persistence or discontinuation).

Assessment of the filgotinib maintenance dose during follow-up will also be done in the subgroup of patients at high risk of MACE, VTE, or malignancy. In addition, the average daily dose during the maintenance period and the duration of use during the follow-up period will be reported.

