Immunomodulators /- suppressants (e.g. tacrolimus, azathioprine, mercaptopurine)	yes	yes	yes	
Other (aminosalicylates, corticosteroids)	yes (not always available; might be in medical report)	yes	yes	
Reasons for switching	yes	yes	yes (SWIBREG, good coverage for targeted therapies)	
Intolerance/adverse events	yes	yes	yes	
Lack of efficacy	yes	yes	yes	
Other	yes	yes	yes	
SmPC section 4.1: Indication				
Severity of UC (moderate to severe)	yes (some data in ENEIDA may be available or alternatively through chart abstraction [through proxies such as drug switching, addition of drugs, colectomy etc.])	yes (SCCAI, CRP, fecal calprotectin and if available radiologic and endoscopic information)	yes (Severity of UC based on proxies such as exposure to immunomodulators or different lines of targeted therapies (= moderate to severe UC) or proxies for flares (e.g., steroid prescriptions, steps in the treatment ladder, hospitalizations with UC as main diagnosis, UC-related surgery, extent/location of	

Variable	Availability in individual registries yes/no (additional comments)			
	ENEIDA (ES)	ICC (NL)	SWIBREG (SE)	
			disease in UC, history of prior biologic use, disease duration and UC-related treatment exposure)	
Date of severity assessment	yes (if defined by medical therapies)	yes	yes	
Date of filgotinib initiation (to ascertain new users) = index date	yes	yes	yes	
Age at index date	yes	yes	yes	
SmPC section 4.2: Posology (Induction treatment)				
Initial filgotinib dose (induction treatment)	yes (if not available, might be in medical report)	yes	yes	
SmPC section 4.3: Contraindications				
Active TB at index date	yes (if not available, might be in medical report)	yes	yes (SmiNet, Population Register)	
Dx date TB	yes (if not available, might be in medical report)	yes	yes (SmiNet, Population Register)	
Active serious infection (SI) at index date	yes (if not available, might be in medical report)	yes	yes (Population Register, PDR)	
Dx date SI	yes (if not available, might be in medical report)	yes	yes (Population Register, PDR)	
Current pregnancy at index date	yes (if not available, might be in medical report)	yes	yes (Medical Birth Register)	

Variable	Availability in individual registries yes/no (additional comments)				
	ENEIDA (ES)	ICC (NL)	SWIBREG (SE)		
Date of pregnancy	yes	yes	yes (Medical Birth Register)		
SmPC section 4.4: Special warnings and precautions for use (Box warning)					
(Age 65+)	yes	yes	yes		

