Variable	Availability in individual registries yes/no (additional comments)		
	ENEIDA (ES)	ICC (NL)	SWIBREG (SE)
			hospitalizations with IBD as the main diagnostic listing will be treated as flares)
Date of hospitalization	no (might be in medical report)	yes	yes (NPR)
Hx of blood clotting disorder or blood clots	no (might be in medical report)	yes (as part of medical history/comorbidity)	yes (NPR)
Concomitant use of combined hormonal contraceptives	no (might be in medical report)	no (but can be added)	yes (NPR)
Concomitant use of hormone replacement therapy	no (might be in medical report)	no (but can be added)	yes (NPR)
SmPC section 4.6: Fertility, pregnancy and lactation			
Advice on contraception in women of childbearing potential	no	no	no
Breastfeeding	no (might be in medical report)	no (but can be added)	no
	Variables assessed during follo	w-up	
Filgotininb treatment status			
Discontinuation	yes	yes	yes (SWIBREG, PDR)
Date of discontinuation	yes	yes	yes (SWIBREG, PDR)
SmPC section 4.2: Posology (Maintenance treatment)			
Maintenance filgotinib dose (after a maximum of 22 weeks of induction treatment)	yes (if not available, might be in medical report)	yes	yes (PDR)
SmPC section 4.3: Contraindications			

Variable	Availabil (ad		ries
	ENEIDA (ES)	ICC (NL)	SWIBREG (SE)
Tuberculosis (TB)	yes (if not available, might be in medical report)	yes	yes (SmiNet)
Dx date TB	yes (if not available, might be in medical report)	yes	yes (SmiNet)
Serious infection (SI)	yes (if not available, might be in medical report; a proxy definition of infection severity can be used to align with the definition of the other registries, based on information available from an eCRF field on the outcome of the infection [such as death, hospital admission])	yes (infections that lead to hospitalization or intravenously administrated antibiotic or antiviral medication)	yes (ICD-10 codes as recorded in the NPR or the 'infectious disease register' [for tuberculosis] including overall codes for e.g. sepsis or septic shock or for specific infectious disease categories being the main or contributory diagnostic listing for a hospitalization)
Dx date SI	yes (if not available, might be in medical report)	yes	yes (NPR)
Pregnancy	yes (if not available, might be in medical report)	yes	yes (Medical Birth Register; could be retrieved following child birth)
Date of pregnancy	yes	yes	yes (Medical Birth Register; could be retrieved following child birth)

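### Section 8.3.3.3 counts every Swedish dispensing as 180 days of use and does not say that a recorded stop date or a new dispensing ends it, so duration is overstated where end of use comes from dispensings alone

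*Protocol*

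**What the plan says.** Section 8.3.3.3 names the PDR as the source of Swedish filgotinib exposure and fixes the length of each dispensing: "A dispensing will be assumed to last for 180 days, after which a lack of a new dispensed prescription will be counted". The sentence goes on to class such a lapse as a treatment hiatus. The section mentions neither quantity dispensed, nor a stop date, nor a change of strength.

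Other places bear on the end of use:

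- Section 8.2.4 runs follow-up from the index date "until the earliest of treatment discontinuation, study withdrawal" or end of study.
- For discontinuation and its date, the Swedish entry in Annex 3 Table 5 names two sources: "yes (SWIBREG, PDR". It gives no order of precedence.
- Section 8.4.3 says that Swedish data on "treatment will be based on data from SWIBREG and the Swedish Patient and Prescribed Drug Registers". Section 8.4.3.1 calls SWIBREG the main data source.
- Table 5 defines the dose variable as "Maintenance filgotinib dose (after a maximum of 22 weeks of induction treatment" (closing bracket omitted). The PDR is the only Swedish source named for it.
- For patients aged 65 or older or at higher risk, Section 6 gives "200 mg once daily for the induction treatment which may be prolonged up to Week 22", then 100 mg once daily. It allows escalation to 200 mg in a flare.
- Section 8.7 (Follow-up) says that "the average daily dose during the maintenance period and the duration of use during the follow-up period will be reported", and it plans a look at maintenance dose in the high-risk subgroup.

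The other two registries work differently. ENEIDA records the end date of the prescription (Section 8.3.3.1), and ICC counts use between the recorded start and stop dates (Section 8.3.3.2).

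**The concern.** The 180-day length is a definition in the protocol itself. Applied as written, it makes a patient with one short supply look the same as a patient who took the drug for almost six months. It also carries every Swedish dispensing beyond Week 22, the point after which Section 6 moves high-risk patients to the lower dose.

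Compliance with posology and duration of use is a named objective in Section 7, and duration is a reported result. In the affected patients, early stopping would read as longer use. Because the other two registries have recorded end dates, part of any Swedish difference in duration could come from the definition. Section 8.1 gives consistency across the registries as a reason for the common protocol.

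There is a second, weaker effect on dose. If the strength of an induction dispensing is carried forward through its 180 days, a high-risk patient who stopped during induction could appear on 200 mg after Week 22.

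**Working it through.** The protocol states 180 days as an assumption and derives it from nothing, so there is no figure of its own to reproduce. The check is day arithmetic.

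**Inputs from the protocol**
- Length of one Swedish dispensing: 180 days (Section 8.3.3.3).
- Upper limit of 200 mg induction in high-risk patients: Week 22 (Section 6).

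**Input not in the protocol**
- Days of supply per dispensing, S. Values of 30, 60, 90 and 180 days are assumed to show the range.

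**Step 1: against Week 22.** 22 × 7 = 154 days. 180 / 7 = 25.7 weeks. 180 − 154 = 26 days.

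A dispensing on day d counts as use to day d + 180. Since d ≥ 0, this always exceeds 154, and the carry-over past Week 22 is d + 180 − 154 = d + 26 days:

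| Last dispensing (day) | Counted end (day) | Days past Week 22 |
|---|---|---|
| 0 | 180 | 26 |
| 30 | 210 | 56 |
| 60 | 240 | 86 |
| 90 | 270 | 116 |
| 120 | 300 | 146 |

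**Step 2: lowest possible duration.** With end of use set from dispensings alone and no earlier censoring (death, withdrawal, loss to follow-up, end of study), the shortest duration is 0 + 180 = 180 days. For a single dispensing on day 0, the ratio of counted to true duration is 180 / (true stop day): 3.2 at day 56, 2.1 at day 84, 1.6 at day 112 and 1.2 at day 154.

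**Step 3: overstatement in general.** Excess = 180 − days actually used after the last dispensing. For a patient who uses up the last supply, that is 180 − S. With true use T, the last dispensing falls on day T − S and counted use is T − S + 180:

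| S (assumed) | Excess (days) | T = 180 counted as (ratio) | T = 360 counted as (ratio) |
|---|---|---|---|
| 30 | 150 | 330 (1.83) | 510 (1.42) |
| 60 | 120 | 300 (1.67) | 480 (1.33) |
| 90 | 90 | 270 (1.50) | 450 (1.25) |
| 180 | 0 | 180 (1.00) | 360 (1.00) |

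**Step 4: with a recorded stop date applied.** The excess is zero. A patient who stops on or before day 154 then contributes no days after Week 22.

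**The case against.** The best reply is that the protocol already provides the stop date. Table 5 lists SWIBREG first for discontinuation and its date, Section 8.4.3.1 calls SWIBREG the main source and says the PDR allows dispensings to be confirmed, and Section 8.2.4 ends follow-up at discontinuation. Source precedence is ordinary material for the analysis plan, and Section 8.7 lets that plan modify the analysis. Much of this stands. A reader might infer that duration is overstated for every Swedish patient, and the documents do not support that. The point is limited to patients dated from dispensings alone. They may be few, since Table 5 claims "SWIBREG, good coverage for targeted therapies" for the reasons for switching. What remains is that the exposure section names only the PDR and fixes the 180 days itself.

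A second reply is that the text calls a lapse a hiatus, not a discontinuation, so 180 days may be meant as a persistence window. That is a sensible use of the figure, and the fix keeps it. But the sentence says how long a dispensing lasts, which is assumed use and not only a tolerated gap.

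Third, a reader might infer that the rule turns correct stopping into non-compliant dosing in high-risk patients. That goes too far. It needs a high-risk patient who stops in induction, a last dispensing of 200 mg, no stop date applied, and a carry-forward of strength that the protocol does not state. Even then, 200 mg after Week 22 is not in itself non-compliant, because Section 6 allows escalation for flare.

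Fourth, the excesses of 90 to 150 days rest on assumed supply lengths. That is correct, and at a true supply of 180 days the excess vanishes.

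**Conclusion.** The point holds in a limited form. Section 8.3.3.3 fixes a length of use that depends on neither quantity nor a recorded stop, and the protocol does not say how it gives way to the SWIBREG discontinuation date. The result that needs no outside figure is the floor of 180 days, 26 days beyond Week 22, for Swedish patients dated from dispensings alone and not censored earlier. Any larger figure depends on the supply per dispensing, which the protocol does not give.

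The effect on maintenance dose in high-risk patients is a possibility only, for the reasons given above. No direction is claimed for average daily dose. The study is descriptive, one registry of three is involved, and the share of patients affected is unknown. The unseen analysis plan may already set a precedence rule. Severity: minor, to be considered.

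**What to change.** In Section 8.3.3.3, add two or three sentences to this effect:

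- Exposure ends at the SWIBREG discontinuation date where one is recorded. Otherwise it ends at the last dispensing plus its dispensed days of supply at once-daily dosing.
- A new dispensing supersedes the earlier one for dose.
- The maintenance dose is taken only from supply that runs past Week 22. A patient with no such supply has no maintenance dose to report.
- 180 days is kept as the permitted gap between dispensings and as a sensitivity analysis for duration.

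The cost is slight extra programming, using sources that the protocol already names. It assumes that the PDR extract carries the quantity dispensed, which the protocol does not state and which should be confirmed. The downside is that patients with no recorded stop date who refill late or hold leftover tablets may be misdated by the difference. The 180-day sensitivity analysis would show how much that matters.

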## 8.4. Data Sources

The study will include information from 3 IBD registries described in more detail below.

## 8.4.1. ENEIDA (ES)

#### 8.4.1.1. Study Main Data Source: the ENEIDA Registry

ENEIDA is a large, prospectively maintained registry of patients with IBD in Spain established in 2005 (Zabana et al., 2020). It is conducted under the auspices of a national scientific society devoted to the study of IBD (the Grupo Español de Trabajo en Enfermedad de Crohn y Colitis Ulcerosa [Spanish Working Group on Crohn's disease and Ulcerative Colitis] GETECCU). Data in the ENEIDA registry come from a network of more than 90 academic and community gastroenterology practices across Spain that have an interest in IBD. As of February 2023, the registry's entire census of patients with UC was 37865, of which >30000 were on active follow-up. Participation in the registry is voluntary for both physicians and patients, and physicians who contribute data to ENEIDA receive no payment for this registry work. The ENEIDA registry is stored in a password-protected MySQL database that is maintained in a secure server facility and managed by dedicated data managers. The investigator or a qualified designee is responsible for verifying the accuracy of patient data as data are entered into the ENEIDA registry.

Participating sites enter data into an electronic case report form (eCRF), which is immediately uploaded in the central ENEIDA registry. Automated data in ENEIDA comprise a predefined set of clinical variables. The registry mandates completion of a limited number of fields on the eCRF, while completion of other fields is optional.

The general organization of data sources, research team, and the flow of information for the study is presented in Figure 1.

#### Figure 1 Organization and Flow of Study Data for ENEIDA

AE = adverse event; ENEIDA = National Study on Inflammatory Bowel Disease Genetic and Environmental Determinants; GETECCU = Spanish Working Group on Crohn's disease and Ulcerative Colitis; PI = principal investigator; RTI-HS = RTI Health Solutions.

#### 8.4.1.2. List of Critical Variables and Calculation of Variable Completeness

ENEIDA sites are expected to record a set of critical variables for each registered patient. On a monthly basis, ENEIDA assesses the completeness of data for each contributing site for all registry patients, not just the patients seen in the clinic that month. Sites with low data completion are asked, but not compelled, to be more thorough.

The critical variables are grouped into the following categories:

- 1. Demographic data: date of birth, sex, date of inclusion in the registry, date of the last visit;
- 2. Clinical data: date of the first diagnosis of UC, current diagnosis (in case the IBD diagnosis changed since presentation), and disease location (at least if on a colonic segment);
- 3. Immunosuppressive therapy (yes or no, and at least 1 drug must be included if answer is "yes");
- 4. Biologic/advanced therapy (yes or no, and at least 1 drug must be included if answer is "yes");
- 5. Surgical treatment (yes or no, and at least 1 type of surgery must be included if answer is "yes").

Details of variables to be collected in ENEIDA can be found in Annex 3 – Table 5.

Calculations of percentage of data completeness include all patients registered within a site, except for sections on details of treatments (i.e. 3, 4, and 5 from the list above) that refer only to patients who received the corresponding therapies. Note that if a single critical variable in a specific section is missing, the entire section is considered to be incomplete. Each site then receives scores for completeness for each section of critical data.

Contributing sites are judged to be of research quality based on the proportion of "complete patients" from that center, i.e. the proportion of patients who have all the predefined "critical variables" completed. To define a center as a "research-quality center" an ad hoc proportion of complete patients (e.g. 95%, 90%, 85%) is selected as the threshold.

Overall, as of June 2022, 55 sites across Spain could be considered of research quality in the ENEIDA registry, based on the definition above and a threshold of 90% completeness of critical variables. Among these, 28 sites had enrolled >1,000 patients each in the ENEIDA registry, representing 78% of patients with UC in the registry.

#### 8.4.1.3. Study Complementary Data Source: Medical Chart Abstraction

The information collected in the ENEIDA registry can be supplemented by the participation of clinical investigators at individual sites in studies where additional information is collected via electronic questionnaires. These questionnaires may collect information on variables that are not recorded in the ENEIDA registry or for which a large number of missing values is expected. Questionnaires can also be used to validate study endpoints and exposure to the drugs of interest that are identified in the ENEIDA automated registry via comparison with patient EMRs.

For the present study, a specific informed consent (IC) of patients will be required to access their EMRs (see also Section 9.3.1) since most of the questions of interest of this PASS fall outside the scope of the information collected by ENEIDA.

## 8.4.2. ICC (NL)

The ICC is a Dutch IBD research organization, which facilitates, coordinates, and conducts collaborative collection of data and biomaterials as well as IBD studies in the Netherlands. It has established a web-based observational, multicenter registry (the "ICC Registry") where patients with an established diagnosis of IBD (both, CD, and UC) are eligible. The study population in the registry includes all patients with IBD 16 years or older who start novel registered drugs in the Netherlands for IBD in routine care. Collected data will consist of routine care data only.

Approximately 20 centers, specialized in IBD will participate in this project, each treating roughly 30 patients with novel IBD medication in academic centers and 10 patients in district hospitals a year. All patients using filgotinib in the participating centers from 2022 onwards will be included in a prospective approach. Furthermore, the ICC drug surveillance program is divided into 2 parts: a retrospective part, from January 2014 until February 2018, and a prospective part starting in March 2018. All information will be stored for 15 years.

No additional interventions besides standard patient care are required for this study and therefore there is no additional burden or risk for patients participating in this study. The scheme set-up to standardize follow-up in participating hospitals is adapted from current guidelines and common practice. Clinical, biochemical, and adverse event (AE) data will be extracted from the patient files. All patient data is stored coded and for the retrospective part it is anonymous in the registry system MEMIC (Center for data and information management at the Faculty of Health, Medicine and Life Sciences of Maastricht University; see also Section 8.6.2). ICC aims to perform an

observational, coded registry without extra interventions to obtain data on the effectiveness in a standard patient-care setting.

